[name], ABPP

Professor
Florida International University
[name]
[name]
[contact]
[contact]

July 16th, 2025

To whom it may concern,

The following study protocol and statistical analysis plan are submitted in reference to NCT03643848 for R01MH116005, Sleep-dependent Negative Overgeneralization in Peripubertal Anxiety.

Aim 3 of this grant was considered a clinical trial at the time it was funded due to random assignment and experimental manipulation. Aims 1 and 2 of the grant were observational and were not considered a clinical trial. The protocol and analytic plan presented here are therefore focused on Aim 3. The primary outcomes for the clinical trial included memory outcomes at 1 week and 12 hours, as detailed in clinicaltrials.gov and the analytic plan. Individual data from the trial and the rest of the project are available via NIMH Data Archive.

Sincerely,

A handwritten signature in black ink, appearing to read '[name]'.

[name], ABPP (PI; contact)

Protocol (Aim 3 of R01MH116005)

Objectives.

Our primary objective is to test the malleability of memory processing during sleep in anxious youth. Specifically, we aim to override the selective replay of negative memories during sleep through competitive displacement, utilizing cued audio reactivation of neutral stimuli relative to sham cueing during NREM sleep. We anticipate this will reduce negative overgeneralization in peri-pubertal youth with clinical anxiety.

Design.

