We will conduct a double-blind randomized design to examine the effects of Targeted Memory Reactivation (TMR) relative to Sham during NREM sleep on negative overgeneralization in youth with anxiety. Sixty youth diagnosed with Social, Separation, and/or Generalized Anxiety Disorder will first undergo clinical assessment and a 7-10 day baseline evaluation of sleep patterns. Participants will then complete an encoding session (referred to as the 'Study' session) in an MRI scanner. Subsequently, they will travel to the sleep lab at Nicklaus Children's Hospital for polysomnography (PSG) hook-up. Following PSG setup, participants will be randomly assigned to either the TMR (n=30) or sham reactivation (n=30) group by an independent research assistant operating from a control room. To maintain double-blinding, participants and the research assistant directly interacting with them will remain unaware of group assignment for the duration of the study. During PSG-monitored NREM sleep, previously-paired neutral sounds from the encoding session will be replayed in the TMR group. In contrast, for the sham group, guitar strums will be played during NREM sleep. Memory outcomes will be assessed at two post-sleep time points: an initial behavioral assessment approximately 11-12.5 hours after the encoding session, and a final assessment approximately 1 week later (between 11 am and 3 pm) conducted in the MRI. More detailed methods for each of these sessions are provided below. Analyses will compare the effects of neutral TMR (relative to sham) on negative and neutral generalization at both the 12-hour and 1-week delay assessment points.

Methods .

Participants. A total of 60 children between the ages of 10 and 13 years will participate in Aim 3, beginning in the 4th year of the broader project period. Participants will be recruited from specialty child mental health clinics at FIU and Nicklaus Children's Hospital as well as via community advertisements.

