
Emotional Memory Task Protocol. As in past studies and our preliminary data, negative overgeneralization will be assessed by the administration of an emotional memory task that lasts approximately ~20 minutes (two ~10-minute runs) during the Study session and ~40 minutes (four ~10-minute runs) during Test sessions. BOLD fMRI data will be collected during the Study session and at the Test session following a 1-week delay. During the task, images (negative, neutral) are presented in the center of the screen on a black background for 2.5 seconds. Simultaneously, semantically related auditory cues will be presented and co-terminate with the visual stimulus. A variable duration (4-9 seconds) fixation cross is displayed in the center of the screen on a black background during the inter-trial-interval. During the Study session participants will undergo an incidental encoding task where they are shown images in a randomized order and asked to rate the images for their emotional valence (negative, neutral). Test sessions follow at both a 12-hour delay and 1-week delay. During the Test sessions, participants will see session specific stimuli that were presented to them during the encoding phase (targets), new stimuli (foils), and stimuli that are similar to the ones seen at encoding but not identical (lures). Emotional valence and similarity level will be evenly distributed across the targets, lures, and foils. Participants will be asked to indicate whether the image they are currently viewing is “old” or “new” with a button press. Instructions during the retrieval phase will explicitly indicate that only the exact image that was presented during the Study phase can be called “old.” Thus, responding to critical lures (“false alarms”) will provide a signature of generalization within each participant. A total of 175 images will be presented during the Study phase and 266 images will be presented during the Test phases. Sixteen (8 neg) of the original 175 images presented during the Study phase will be tested at the 12-hour Test session along with 30 lures (15 neg) and 24 foils (12 neg); 44 study images (22 neg) will be tested at the 1-week Test session with 85 lures (43 neg) and 67 foils (31 neg).

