Primary Hypothesis (1 week outcomes): We expect audio cueing of neutral memories relative to sham cueing will result in decreased Lure Generalization Index (LGI) for negative stimuli and increased LGI for neutral stimuli at one week. To test these hypotheses, we will employ a mixed-effects model. The dependent variable will be the Lure Generalization Index (LGI) at 12 hours. The model will include fixed effects for valence (neutral vs. negative stimuli), experimental condition (neutral Targeted Memory Reactivation [TMR] vs. sham), and their interaction term (valence x condition). A random subject effect will be included to account for individual variability. Age (months) and gender will also be included as fixed effects to control for known gender and developmental differences in sleep, memory and anxiety. Should the valence by condition interaction prove statistically significant, we will conduct planned post-hoc comparisons (using t-tests with the Welch-Satterwaite equation) to thoroughly investigate the directionality and magnitude of the effects for LGI across the different valence categories and experimental conditions.

Secondary Hypothesis (12 hour outcomes): We will apply the same analytical approach as described for the 1-week outcomes to the 12-hour outcomes. We expect to observe a similar pattern of results, though with a smaller effect size.

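### The primary model's random subject effect cannot represent a negative correlation between a child's two LGI values; if that correlation is negative within arms, the interaction test is anticonservative, and a one-line covariance change removes the risk at no cost

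*Combined protocol and SAP*

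**What the plan says.** Under Statistical Plan, Primary Hypothesis (1 week outcomes), LGI is modelled with fixed effects for valence, condition and their interaction. On covariates it adds: "Age (months) and gender will also be included as fixed effects". The only term that ties together the two values from one child is described as follows: "A random subject effect will be included to account for individual variability". No covariance structure, rule for a zero variance estimate, degrees-of-freedom method or software is named.

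Each analysis uses one time point, so a child contributes two values. (The paragraph on the 1-week hypothesis states "The dependent variable will be the Lure Generalization Index (LGI) at 12 hours". That is a separate inconsistency, and there are two values per child at either time.) Post-hoc comparisons follow only if the interaction is significant, and the Secondary Hypothesis paragraph applies the same approach to the 12-hour outcomes. Protocol, Design sets the group sizes: "TMR (n=30) or sham reactivation (n=30) group".

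On mechanism, Protocol, Objectives says that the aim is to "override the selective replay of negative memories during sleep through competitive displacement". The primary hypothesis expects "decreased Lure Generalization Index (LGI) for negative stimuli and increased LGI for neutral stimuli at one week". No part of the documents states a correlation between a child's negative and neutral LGI.

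**The concern.** With one random intercept and two values per child, the modelled correlation is the subject variance divided by the sum of subject and residual variance. It cannot fall below zero. If the true within-arm correlation is negative, the fit goes to the boundary and treats the 120 values as independent. The interaction is a contrast of within-child differences, and a negative correlation makes those differences more variable than independence allows. The model standard error is then too small.

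The sign cannot be settled from the documents. If negative and neutral memories compete for replay and children differ in the balance, the correlation is pushed down. If children differ in overall memory ability or in readiness to answer that an image is old, it is pushed up. At stake are the false-positive rate and the confidence interval of the one test on which the follow-up comparisons depend.

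**Working it through.** The plan gives no alpha, power, standard deviation or correlation, so it has no figure to reproduce.

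**Inputs.** From the documents: 30 children per arm, two values per child, and age and gender as child-level covariates. Assumed: two-sided 5%, normal errors, complete pairs, equal variance σ² for the two valences, and within-arm correlation ρ as shown.

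**Large-sample size.**
- The within-child difference has variance 2σ²(1 - ρ), so the interaction estimate has variance 2 × 2σ²(1 - ρ)/30 = 4σ²(1 - ρ)/30.
- With the subject variance at zero, the model uses about 4σ²/30. The ratio of model to true standard error is 1/√(1 - ρ).
- At ρ = -0.3 and σ = 1, the true SE is √(5.2/30) = 0.416 and the model SE is √(4/30) = 0.365, a ratio of 0.88.
- Type I error is 2 × [1 - Φ(1.96/√(1 - ρ))]. At ρ = -0.3, 1.96/√1.3 = 1.72, which gives 8.6%. At -0.2 and -0.1 it is 7.4% and 6.2%.

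**Finite-sample check.** For balanced data REML has a closed form. The within-child mean square has 60 - 2 = 58 df, and the between-child mean square has 60 - 4 = 56 df after intercept, condition, age and gender. If the between-child mean square is the larger, the interaction is tested on the within-child one with 58 df. If not, the subject variance is zero and the two are pooled on 58 + 56 = 114 df. Results from 200,000 simulated null trials per setting:

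| ρ, both arms | Subject variance estimated as zero | Type I error, planned model | Type I error, within-child difference |
|---|---|---|---|
| +0.3 | 1% | 5.0% | 5.0% |
| +0.1 | 23% | 5.1% | 5.0% |
| 0 | 50% | 5.6% | 5.0% |
| -0.1 | 78% | 6.4% | 5.1% |
| -0.2 | 94% | 7.3% | 5.0% |
| -0.3 | 99% | 8.4% | 5.0% |
| -0.5 | 100% | 10.7% | 4.9% |

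Repeat runs gave 6.3-6.5% at -0.1, 7.2-7.4% at -0.2 and 8.4-8.5% at -0.3. The result is not a product of the change in df: keeping 58 df after truncation still gives 8.1% at -0.3. Direct REML fits with age and gender (3,000 trials per setting, Monte Carlo SE about 0.4 percentage points) gave 8.3% at -0.3 and 8.0% at -0.2. Compound symmetry allowing negative correlation gave 4.6% and 5.5% in the same trials.

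**Negative correlation in the TMR arm only.**
- Sham +0.3, TMR -0.3: 5.6%.
- Sham +0.3, TMR -0.5: 6.3%.
- Sham 0, TMR -0.3: 6.7%.

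**Do opposite mean shifts create the problem?** Take a within-arm correlation of +0.3 and between-arm shifts of 1.5 SD in opposite directions. Pooled over two equal arms, the covariance is 0.3 - 0.75² = -0.2625 and each variance is 1 + 0.75² = 1.5625, so the pooled correlation is -0.2625/1.5625 = -0.17. The condition and interaction terms remove these shifts. The within-arm correlation, which is what the random effect models, stays at +0.3.

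**The case against.** A reader might infer that the trial's own competition theory implies a negative correlation, so that the primary test is invalid in exactly the scenario the mechanism predicts. The documents do not support this. The displacement they describe is produced by cueing and is stated as opposite mean shifts between arms, which the fixed effects absorb. Sham children receive no neutral cues. Under a null of no cueing effect there is no cue-driven displacement in either arm. If displacement varied around a zero mean among TMR children only, the inflation would be the smaller 5.6-6.7%. The figures of 7% and above need a negative correlation in both arms, hence natural competition for replay that differs between children. That is plausible, but it is not stated.

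There are also reasons to expect a correlation near or above zero. Both values come from one child's old/new responses in one session, and the Emotional Memory Task section says that false alarms to lures "will provide a signature of generalization within each participant". A general readiness to answer old could raise both, although the LGI formula is not given. Item noise also pulls an observed correlation towards zero. As an illustration, assume that LGI is a simple lure false-alarm rate with mean 0.4 and between-child SD 0.15. With 15 lures per valence at 12 hours, reliability is about 0.0225/(0.0225 + 0.24/15) = 0.58, so an observed -0.3 needs a latent correlation near -0.5. With 42 or 43 lures per valence at 1 week, it needs about -0.38.

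Finally, a random intercept for two repeated measures is conventional, and some implementations allow negative covariance. The between-arm Welch comparisons within one valence do not use this correlation.

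All of this stands, and it limits the point to a conditional one. It does not remove it: the usual reading of the sentence imposes the bound, nothing in the plan guards against it, and the Welch comparisons are reached only through the affected test.

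**Conclusion.** The point holds as a conditional weakness and a free improvement; it is not a demonstrated error. If the within-arm correlation is negative in both arms, the interaction test at a nominal 5% runs at roughly 6.3% to 8.5% for correlations from -0.1 to -0.3. If it is +0.1 or more, the test is essentially correct (about 5.0-5.3%). At exactly zero there is a slight excess, about 5.6%, because the variance is truncated in half of all trials. These figures rest on the assumed alpha and correlations, complete pairs, and reading the random subject effect as an intercept with non-negative variance. The documents do not show which sign applies.

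**What to change.** In the Statistical Plan, keep the fixed effects and replace the random subject effect by an unstructured 2x2 covariance for the two valences within child, or by compound symmetry that allows negative covariance. Equivalently, test the arm difference in each child's negative-minus-neutral LGI on 58 df; age and gender, entered as common child-level effects, cancel from that difference. Name the degrees-of-freedom method, and apply the same structure at 12 hours and 1 week.

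The cost is one line of text and one model option. With complete pairs and a positive estimated subject variance, the interaction test is identical to the planned one on the same 58 df. When the variance estimate would be zero, the change restores the nominal error rate (4.9-5.1% across the correlations tried).

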The 10-13 year age range is aligned with peri-puberty and allows for the study of sleep-dependent mechanisms of overgeneralization prior to the steep escalation of emotion-related disorders through mid-late adolescence (peaking from 16-18 years). In line with the RDoC framework, we will sample across a continuum of anxiety severity to capture variability on emotion reactivity and sleep neurophysiology during this sensitive period of development, while minimizing developmental variability in the sample. We will focus on symptoms of Separation Anxiety Disorder (SAD), Social Phobia (SP), and Generalized Anxiety Disorder (GAD) based on phenotypic overlap in emotion responding and sleep across these diagnostic categories and comorbidities. The proposed framework has implications for other disorders characterized by

negative emotions and sleep disruptions, such as OCD and Panic Disorder. Given high comorbidity with GAD, SAD, and SP, we do allow for elevated symptoms in these diagnostic categories. However, we exclude those who meet full diagnostic criteria for these disorders because they show somewhat less phenotypic overlap with SAD, GAD and SP in sleep and emotion response profiles and it is important to balance generalizability of findings with precision of investigation at this stage of inquiry. Extensive efforts will be made to prevent attrition and optimize parent and child participation. Parents of children will be compensated up to \$300 for completion of the study.

Intake, Screening and Baseline Characteristics. Following a brief phone screen to verify potential inclusion (e.g. no braces, within age range etc.) eligible families will be scheduled for consent and assessment to verify group inclusion/exclusion criteria. Inclusion and exclusion criteria are detailed further in clinicaltrials.gov entry.

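### Do the age and gender main effects fail to control the valence-by-condition test that opens the follow-up comparisons?

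*Combined protocol and SAP*

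**What the plan says.** Under the Primary Hypothesis in the Statistical Plan, LGI is modelled with fixed effects for valence and condition "and their interaction term (valence x condition"). Within-child correlation is handled by one random term: "A random subject effect will be included to account for individual variability". The covariates follow: "Age (months) and gender will also be included as fixed effects to control for known gender and developmental differences in sleep, memory and anxiety". No product of age or gender with valence or condition is named.

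The interaction acts as a gate: "Should the valence by condition interaction prove statistically significant, we will conduct planned post-hoc comparisons (using t-tests with the Welch-Satterwaite equation"). For the secondary hypothesis, "We will apply the same analytical approach as described for the 1-week outcomes to the 12-hour outcomes".

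Two design facts matter. Condition varies between children, 30 per arm (Design). Valence varies within child, because every child is tested on both negative and neutral lures (Emotional Memory Task Protocol). On the sample, the Participants section says that the 10-13 year range serves to study peri-puberty "while minimizing developmental variability in the sample".

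**The concern.** A reader who sees two covariates entered for a stated purpose expects them to do something in the test that matters most. Here that is the interaction, because without a significant interaction no follow-up comparison is made, at 1 week or at 12 hours. Age and gender take the same value in both of a child's rows, so as main effects they have no leverage on a within-child contrast. If the follow-ups are ordinary Welch tests on raw scores, those carry no covariates either. The adjustment would then reach neither decision step, and a report could describe the key result as controlled for age and gender when the covariates had not altered it.

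At stake would be precision, and accuracy of description. Bias and type I error are not in question, because condition is randomised.

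**Working it through.** **Inputs.** From the documents: 60 children, 30 per arm; valence within child, condition between children; the model terms above. Assumed: one LGI value per valence per child (the index formula is not given), a random intercept, and age and gender as main effects. The plan gives no alpha, power, SD or effect size, so there is no figure of its own to reproduce.

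**Step 1: the cancellation.** For child i and valence v (0 or 1), with condition c:

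y_iv = b0 + b1·v + b2·c_i + b3·v·c_i + g1·age_i + g2·gender_i + u_i + e_iv

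Subtracting one valence from the other within a child gives

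d_i = b1 + b3·c_i + (e_i1 − e_i0).

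Age, gender and the subject effect u_i all drop out. With complete pairs and a positive subject variance, the test of b3 is the two-sample t-test on d_i with 60 − 2 = 58 df.

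Simulation agrees. In 200 data sets per setting, adding age and gender changed the interaction estimate by less than 1e-15 and, where the subject variance was above zero, its SE by a relative 3e-8 at most. In one data set the estimate was −0.126522 (SE 0.059851) without covariates, with them, and from the difference scores.

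**Step 2: what the cancellation means.** The terms g1·age_i and g2·gender_i are the differences between children that are shared by both valences. They vanish from d_i because each child is his or her own control, so their influence on the test is already removed in full. The covariates are redundant there. All that is left unadjusted is an age or gender effect that differs by valence, and the plan neither asserts such an effect nor promises to adjust for one.

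**Step 3: where the covariates do act.** They act on the condition term (the condition effect at the reference valence). Under the simulation's assumed effects (age slope 0.006 per month, gender 0.10), its SE was 8% to 19% larger without them.

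**Step 4: what the alternative would buy.** Adding age-by-valence and gender-by-valence amounts to regressing d_i on condition, age and gender (56 df). With R² the share of the variance of d_i explained by age and gender,

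SE ratio (alternative / planned) = √[(1 − R²) · 58/56].

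Break-even is R² = 1 − 56/58 = 3.4%. Power is by noncentral t, from an assumed 80% under the plan:

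| R² (assumed) | SE ratio | Power |
|---|---|---|
| 0 | 1.018 | 78.6% |
| 5% | 0.992 | 80.6% |
| 10% | 0.965 | 82.6% |
| 20% | 0.910 | 86.8% |

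A single trial can go either way. The data set in Step 1 was generated with true covariate-by-valence effects (gender 0.10, age 0.004 per month), yet the alternative gave −0.124466 with SE 0.060362, a ratio of 0.060362/0.059851 = 1.009. At a true R² of 5%, the simulated per-trial SE ratio ran from about 0.93 to 1.05 (5th to 95th percentile).

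**Step 5: where the cancellation is not exact.**

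- Subject variance estimated at zero: the estimate still does not move, but the SE can. This occurred in 22% of simulated trials at an assumed intraclass correlation of 0.1 and in 1% at 0.3. At 0.1, the SE ratio from adding the main effects averaged 0.975 in those trials if the covariates explain about 9% of LGI variance.
- One valence missing in 3, 6 or 12 of the 60 children: the estimate moves by a median of 0.04, 0.05 or 0.06 SE (maximum 0.19, 0.25, 0.37).

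In these cases the main effects do reach the gate test, usually slightly.

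**The case for a change.** The strongest case for the concern is that a reader of the Statistical Plan would naturally take the interaction result as adjusted for age and gender. The only kind of age or gender effect that could add noise to that test, one that differs by valence, is the kind the model omits. If R² were 20%, the omission would cost 86.8 − 80 = 6.8 points of power. Age and gender are to be collected anyway, so before analysis the change is one line of text.

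The algebra stands, and so does the conditional gain. What does not follow is that the plan is wrong. The gain depends on an R² that no document supplies, and the restricted age range points towards a small contribution from age. Below 3.4% the change costs power. The cover letter also states "Individual data from the trial and the rest of the project are available via NIMH Data Archive". If the analysis is done, the planned model would stay primary and only an optional sensitivity analysis would remain.

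The plan does leave one thing open: whether the Welch comparisons are run on raw scores or as contrasts from the model. That is a request for clarification, and neither answer changes the interaction test. Simulation also shows type I error of up to 9.7% for within-valence contrasts from an equal-variance random-intercept model, when one valence is assumed to have 1.5 times the SD of the other. The plan does not name that analysis. Welch tests held at 4.7-5.2% in the same settings, so this figure lends the concern no weight.

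**Conclusion.** The concern does not hold. Age and gender main effects do cancel from the valence-by-condition test, but only because pairing has already removed what they would control. The test stays valid under randomisation, and nothing in the plan says that it is adjusted. Adding covariate-by-valence terms is a choice a statistician could reasonably make or decline: from an assumed 80% power it loses 1.4 points if the covariates explain none of the difference and gains 0.6 points at 5%.

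This rests on one LGI per valence per child, a random intercept, complete pairs and a subject variance above zero. Where the last two fail, the main effects act on the gate test to a usually small extent, which weakens the concern further. The conclusion is the same for the 1-week and the 12-hour outcome.
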